7.0 Protocol Treatment

7.1 Treatment Schedule - Use actual weight or estimated dry weight if fluid retention

Agent	Dose	Route	Day	ReRx
Pembrolizumab	200 mg	IV	Day 1	every 21 (+/- 3) days for a maximum of 2 years (approximately 35 cycles)
Imiquimod	5%	Cutaneous	M-F ^{a,b}	

a Regardless of what day of the week the cycle starts, imiquimod is to be administered daily for the remaining weekdays up to and including Friday.

b. At the completion of cycle 2 and cycle 4, a biopsy of the treated lesion will be performed (and if appropriate, a biopsy of an untreated lesion). Imiquimod is not to be administered the day of the biopsy or for six days following the biopsy. If the biopsy is performed on Monday, Imiquimod treatment should be given the following M-F. If the biopsy is performed on Tuesday, Imiquimod treatment should be given the next Tuesday-Friday and then M-F for the remainder of the cycle. If the biopsy is performed on Wednesday, Imiquimod treatment should be given the next Wednesday-Friday and then M-F for the remainder of the cycle. If the biopsy is performed on Thursday, Imiquimod treatment should be given the next Thursday-Friday and then M-F for the remainder of the cycle. If the biopsy is performed on Friday, Imiquimod treatment should be given the next Friday and then M-F for the remainder of the cycle.

- 7.2 Patients can be instructed in administration techniques of imiquimod and granted treatment independence. This training must be documented in medical record. Imiquimod is a commercial product dispensed from the pharmacy and is the same drug that would be prescribed to any other patient not on trial.
- 7.3 Imiquimod will be held for one week after biopsy to allow for proper wound healing.
- 7.4 If more than 1 cutaneous lesion is present, at least one lesion will not be treated with imiquimod to serve as a control for the effect of just pembrolizumab. The untreated lesion must be at least 2 cm from the treated lesion to account for possible treatment effect from the imiquimod on the primary.
- 7.5 Treatment by a local medical doctor (LMD) is not allowed.

8.0 Dosage Modification Based on Adverse Events

8.1 Dose-Modification Guidelines for Drug Related Adverse Events for Pembrolizumab

CTCAE System/Organ/Class (SOC)	ADVERSE EVENT	Hold Treatment for Grade	Timing for Restarting Treatment	Discontinue Subject
Gastrointestinal disorders	Diarrhea/Colitis	2-3	AE resolves to Grade 0-1	Toxicity does not resolve within 12 weeks of last dose or inability to reduce corticosteroid to 10mg or less of prednisone or equivalent per day within 12 weeks.
		4	Permanently discontinue	Permanently discontinue
Investigations	AST, ALT, or Blood bilirubin	2	AE resolves to Grade 0-1	AE does not resolve within 12 weeks of last dose
		3-4	Permanently discontinue (see exception below) ^a	Permanently discontinue
Metabolism and nutrition disorders	Glucose intolerance (Type 1 diabetes mellitus [if new onset] or Hyperglycemia)	Type 1 diabetes mellitus or 3-4	Hold pembrolizumab for new onset Type 1 diabetes mellitus or Grade 3-4 hyperglycemia associated with evidence of beta cell failure.	Resume pembrolizumab when patients are clinically and metabolically stable.
Endocrine disorders	Hypophysitis	2-3	AE resolves to Grade 0-1	AE does not resolve within 12 weeks of last dose or inability to reduce corticosteroid to 10mg or less of prednisone or equivalent per day within 12 weeks
		4	Permanently discontinue	Permanently discontinue
Endocrine disorders	Hyperthyroidism	3	AE resolves to Grade 0-1	AE does not resolve within 12 weeks of last dose or inability to reduce corticosteroid to 10 mg or less of prednisone or equivalent per day within 12 weeks.
		4	Permanently discontinue	Permanently discontinue

CTCAE System/Organ/Class (SOC)	ADVERSE EVENT	Hold Treatment for Grade	Timing for Restarting Treatment	Discontinue Subject
Endocrine disorders	Hypothyroidism	2-4	Therapy with pembrolizumab can be continued while treatment for the thyroid disorder is instituted	Therapy with pembrolizumab can be continued while treatment for the thyroid disorder is instituted.
General disorders and administration site conditions	Infusion reaction	3-4	Permanently discontinue	Permanently discontinue
Respiratory, thoracic and mediastinal disorders	Pneumonitis	2	AE resolves to Grade 0-1	AE does not resolve within 12 weeks of last dose or inability to reduce corticosteroid to 10mg or less of prednisone or equivalent per day within 12 weeks.
		3-4	Permanently discontinue	Permanently discontinue
Renal and urinary disorder	Acute kidney injury or Chronic kidney disease (e.g. Renal failure or Nephritis)	2	AE resolves to Grade 0-1	AE does not resolve within 12 weeks of last dose or inability to reduce corticosteroid to 10 mg or less of prednisone or equivalent per day within 12 weeks.
		3-4	Permanently discontinue	Permanently discontinue
	All Other Drug Related Adverse Events ²	2	AE resolves to Grade 0-1	AE does not resolve within 12 weeks of last dose or inability to reduce corticosteroid to 10 mg or less of prednisone or equivalent per day within 12 weeks
		3-4	Permanently discontinue	Permanently discontinue

* Located at [REDACTED]

NOTE: Permanently discontinue Treatment for any severe or Grade 3 drug-related AE that recurs or any life-threatening event.

^aFor patients with liver metastasis who begin treatment with Grade 2 AST or ALT, if AST or ALT increases by greater than or equal to 50% relative to baseline and lasts for at least 1 week then patients should be discontinued.

^bPatients with intolerable or persistent Grade 2 drug-related AE may hold study medication at physician discretion. Permanently discontinue study drug for persistent Grade 2 adverse reactions for which treatment with treatment with study drug has been held, that do not recover to Grade 0-1 within 12 weeks of the last dose.

8.2 Dose-Modification Guidelines for Drug Related Adverse Events for Imiquimod

CTCAE System/Organ/Class (SOC)	ADVERSE EVENT	Hold Treatment for Grade	ACTION
General Disorders and administration site conditions	Local skin reaction	3	Temporarily interrupt treatment for up to several days for severe or intolerable reactions; may consider resuming therapy once reaction subsides.
	Flu-like symptoms	3	Temporary disruption of therapy

9.0 Ancillary Treatment/Supportive Care

9.1 Full supportive care

Patients should receive full supportive care while on this study. This includes blood product support, antibiotic treatment, and treatment of other newly diagnosed or concurrent medical conditions. All blood products and concomitant medications such as antidiarrheals, analgesics, and/or antiemetics received from the first day of study treatment administration until 30 days after the final dose will be recorded in the medical records.

9.2 Hypersensitivity reactions

Patients do not require premedication prior to pembrolizumab treatment, as hypersensitivity reactions is not expected. In the unlikely event of a hypersensitivity reaction, treatment with antihistamines, H2 blockers, and corticosteroids is recommended. Patients should be pre-medicated with the typical regimen for subsequent cycles.

9.3 Patients may not enroll in a different clinical study, including Cancer Control studies, in which investigational procedures or agents are being used, while participating in this study.

9.4 Patients must terminate study treatment if they are to receive radiation therapy for palliative reasons as it impacts upon assessing response.

9.5 General patient monitoring and supportive care guidelines

9.51 Patients should be carefully monitored during the treatment phase and then followed appropriately. Decisions for retreatment or dose modifications/interruption should follow the guidelines in Sections 8.2.

9.52 Patients who have an ongoing study agent-related serious adverse event upon study completion or at discontinuation from the study will be contacted by the treating physician or his/her designee at least every 2 weeks until the event is resolved or determined to be irreversible.

- 9.6 Side effect management for **PEMBROLIZUMAB** toxicities- these are to be regarded as guidelines for managing toxicity that occurs with pembrolizumab therapy and should not replace clinical judgement (i.e. - patients with grade 1 rash may require systemic steroids).

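### Section 9.51 sends dose decisions only to the imiquimod table, and 9.2 directs premedication for later cycles with no grade limit although 8.1 stops pembrolizumab at grade 3-4

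*Combined protocol and SAP*

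**What the plan says.** Section 9.51, in the general monitoring guidance, reads: "Decisions for retreatment or dose modifications/interruption should follow the guidelines in Sections 8.2". No other section is named there.

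Section 8.2 is headed "Dose-Modification Guidelines for Drug Related Adverse Events for Imiquimod". Its table has two rows, "Local skin reaction" and "Flu-like symptoms", each with a temporary interruption at grade 3. The rules for the systemic drug are in the preceding table, 8.1, headed "Dose-Modification Guidelines for Drug Related Adverse Events for Pembrolizumab".

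Section 9.2 expects no hypersensitivity to pembrolizumab and then provides for it: "In the unlikely event of a hypersensitivity reaction, treatment with antihistamines, H2 blockers, and corticosteroids is recommended". The next sentence is "Patients should be pre-medicated with the typical regimen for subsequent cycles". Neither sentence mentions a grade or refers to Section 8.

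In 8.1 the row "Infusion reaction" lists grade 3-4, with permanent discontinuation in both action columns. The last row, for all other drug-related events, holds at grade 2 and permanently discontinues at grade 3-4. A NOTE under the table also requires a permanent stop for any life-threatening event.

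**The concern.** An investigator handling a reaction to pembrolizumab would naturally turn to Section 9. There, 9.2 says what to give and then speaks of later cycles, whatever the grade. The general instruction on retreatment in 9.51 then leads to a table that has no row for hypersensitivity, for infusion reactions or for any other pembrolizumab toxicity. Neither step leads to the permanent stop in 8.1.

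The two slips therefore reinforce each other. Followed literally and without 8.1 at hand, Section 9 would allow pembrolizumab to be given again, with premedication, after a grade 3 or 4 reaction for which 8.1 ends treatment. This is a matter of patient safety and consistent conduct, not of statistics.

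**Working it through.** No arithmetic applies and the plan gives no figure on this point. The check sets the sections side by side.

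**Step 1: where 9.51 leads.** It cites 8.2 alone, and 8.2 is limited to imiquimod by its title and by both of its rows. I found no other section that refers the reader to 8.1. Section 13.3 lists unacceptable toxicity as a reason to stop but cites no table.

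**Step 2: which 8.1 row takes a hypersensitivity reaction.** 8.1 has no row of that name. Section 10.61 has allergic reaction and anaphylaxis graded at each evaluation, so the plan anticipates such events. A drug-related reaction could be recorded as an infusion reaction or fall into the catch-all row. Both possibilities are shown below.

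| Grade of reaction | 9.2 | 8.1, infusion reaction row | 8.1, catch-all row |
|---|---|---|---|
| 1 | Treat; premedicate later cycles | No action listed | No action listed |
| 2 | Same | No action listed | Hold until grade 0-1, with a 12-week limit |
| 3 | Same | Permanent stop | Permanent stop |
| 4 | Same | Permanent stop | Permanent stop |

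The choice of row does not matter at grade 3-4: both end pembrolizumab. A life-threatening reaction is also stopped by the NOTE. Section 9.2 says the same thing at every grade.

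**Step 3: whether Section 9 normally leaves stopping to Section 8.** Mostly it does. For grade 4 hyperthyroidism (9.632), grade 4 hypophysitis (9.642), pneumonitis of grade 3 or more (9.653) and bilirubin of grade 3 or more (9.673), Section 9 describes management and does not repeat the stop that 8.1 imposes. The exception is 9.663, which repeats the stop for AST or ALT of grade 3 or more. Those four items, however, say nothing about further doses. Section 9.2 gives a positive instruction about later cycles, so the general pattern does not account for it.

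**Step 4: whether an analysis is affected.** The response, safety, progression-free survival and overall survival definitions in 16.2 to 16.4 do not refer to these instructions. The stopping rule in 16.61 counts treatment-related grade 4 events whether or not the patient stops treatment. Nothing in Section 16 needs to change.

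**The case against.** The strongest reply is that this is clerical. Section 8.1 is titled as the pembrolizumab table, stands directly before 8.2, and needs no cross-reference to apply. The plural in 9.51 suggests that a reference to 8.1 was dropped in editing, and nobody would take a two-row imiquimod table for the pembrolizumab rules. As for 9.2, speaking of subsequent cycles presupposes that further cycles are allowed, and 8.1 decides that. Section 9 mostly deals with management and leaves stopping to Section 8.

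Much of this stands. A reader might infer that 9.51 sets 8.1 aside, or that the plan orders re-dosing after severe reactions. The documents support neither: nothing in 9.51 displaces 8.1, and 9.2 can be read consistently with it. What remains is that each harmless reading needs words that the plan does not contain. The clinical-judgement caveat in 9.6 concerns the side-effect guidance under that heading and does not qualify 9.2 or 9.51.

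A reader might also infer a third conflict in 8.1. The hypothyroidism row lets pembrolizumab continue at grades 2-4, while the NOTE requires a permanent stop for a recurrent grade 3 or a life-threatening event and names no exception. That does not justify a required change. The row is permissive and the NOTE can be read as adding a limit to it; equally, the specific row can be read as prevailing. The NOTE is the stricter of the two, so applying it exposes nobody to excess drug, and the documents give no basis for choosing which should govern. It is at most a query to the sponsor.

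**Conclusion.** Wrong as written, on two counts, and minor. Section 9.51 cites the wrong table for the systemic drug. Section 9.2 lacks the grade limit that would make it agree with 8.1. Grades 3 and 4 are where 9.2, taken literally, departs from 8.1.

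The practical size is small: 10 patients are planned (16.1), treatment starts under a medical oncologist (6.9a), and 8.1 remains in force. No planned analysis changes. The correction is still worth making because this is operative safety text, and the misreading it invites is re-dosing after a severe reaction.

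The conclusion assumes that a hypersensitivity reaction to pembrolizumab would be judged drug-related and so fall under one of the two 8.1 rows. It does not assume that any investigator would overlook 8.1, only that Section 9 does not guard against it.

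**What to change.** 1. In 9.51, replace the reference to *Sections 8.2* with *Sections 8.1 and 8.2*.
2. In 9.2, limit the premedication sentence to grade 1-2 reactions and add: *for grade 3-4 reactions, permanently discontinue pembrolizumab per Section 8.1*. The grade 2 hold in the catch-all row of 8.1 can stay as it is.

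The cost is a wording amendment to two sections. It adds no visit, procedure or patient, and Section 16 is untouched.

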9.61 Diarrhea

- 9.611 Grade 1- without abdominal pain/or blood in stool and symptoms, may be caused either by pembrolizumab. Infectious etiologies should be ruled out. Patients may be managed symptomatically, including the use of loperamide. Instruct patients to report any increase in stools.
- 9.612 Grade 2- without abdominal pain/or blood in stool and symptoms < **1 week**, and resolve to grade 0 or 1- continue to monitor. Infectious etiologies should be ruled out.
- 9.613 Grade 2- symptoms >**1 week**, should be started on systemic steroid therapy. Infectious etiologies should be ruled out.
- 9.614 Grade 3 or greater- **who have other etiologies ruled out** should be started on systemic steroids. Assess for dehydration. Patients may require hospitalization for IV steroids followed by oral steroids.

**** Once patients have improvement of symptoms to grade 0 or 1 taper of steroids should occur over at least 1 month- if patients have been started on budesonide in addition to systemic steroids, start tapering the prednisone **FIRST**.**

Do NOT administer loperamide in patients with \geq Grade 2 diarrhea as this may cause toxic megacolon and/or perforation.

If at any time patients experience diarrhea with the following symptoms: fever or abdominal pain patients should have a CT scan of the abdomen to rule out perforation. Emergent surgical evaluation should be performed if perforation is found. If a patient has bloody diarrhea, a Gastroenterology consult should be obtained. A Gastroenterology consult should be obtained if provider is considering infliximab for treatment of colitis.

For all patients- assess hydration status and monitor electrolytes, including magnesium.

9.62 Rash

- 9.621 Grade 2- Initiate therapy with topical or systemic steroids at 0.5-1mg/kg/day of prednisone or equivalent.
- 9.622 Grade 3 or greater. Initiate systemic steroid therapy at 1-2 mg/kg/day of prednisone or equivalent.

- 9.63 Hyperthyroidism
 - 9.631 Grade 3- Initiate systemic steroid treatment at 1-2 mg/kg/day of prednisone or equivalent.
 - 9.632 Grade 4 - Initiate systemic steroid therapy at 1-2 mg/kg/day of prednisone or equivalent.
- 9.64 Immune-Mediated Hypophysitis
 - 9.641 Grade 2 and 3 – Initiate systemic steroid at 0.5-1mg/kg/day of prednisone or equivalent and physiologic replacement dose.
 - 9.642 Grade 4 – Initiate systemic steroid at 1-2 mg/kg/day of prednisone or equivalent and physiologic replacement dose.
- 9.65 Pneumonitis
 - 9.651 Grade 1- No change in treatment
 - 9.652 Grade 2- Initiate steroids at 0.5-1mg/kg/day of prednisone or equivalent.
 - 9.653 Grade 3 or greater- Consider hospitalization, and initiate systemic steroids
- 9.66 Liver Dysfunction (AST or ALT)
 - 9.661 $AST \text{ or } ALT \leq 3 \text{ ULN}$ - No change in treatment
 - 9.662 $AST \text{ or } ALT > 3 \text{ but } < 5 \text{ ULN}$ or Grade 2- Consider initiating systemic steroids at 0.5-1mg/kg/day of prednisone or equivalent.
 - 9.663 $AST \text{ or } ALT \geq \text{Grade 3}$ - Discontinue pembrolizumab. Initiate systemic steroid therapy.
- 9.67 Liver Dysfunction (Bilirubin)
 - 9.671 Grade 1- No change in treatment
 - 9.672 Grade 2- Consider initiating systemic steroids at 0.5-1mg/kg/day of prednisone or equivalent.
 - 9.673 Grade 3 or greater- Monitor levels until resolved to \leq Grade 1. Initiate therapy with steroids at 1-2 mg/kg/day of prednisone or equivalent.

10.0 Adverse Event (AE) Reporting and Monitoring

The site principal investigator is responsible for reporting any/all serious adverse events to the sponsor as described within the protocol, regardless of attribution to study agent or treatment procedure.

The sponsor/sponsor-investigator is responsible for notifying FDA and all participating investigators in a written safety report of any of the following:

- Any suspected adverse reaction that is both serious and unexpected.
 - Any findings from laboratory animal or *in vitro* testing that suggest a significant risk for human subjects, including reports of mutagenicity, teratogenicity, or carcinogenicity.
 - Any findings from epidemiological studies, pooled analysis of multiple studies, or clinical studies, whether or not conducted under an IND and whether or not conducted by the sponsor, that suggest a significant risk in humans exposed to the drug.
 - Any clinically important increase in the rate of a serious suspected adverse reaction over the rate stated in the protocol or Investigator's Brochure (IB).
 - Any outcomes related to pregnancy while on study.
- Summary of SAE Reporting for this study
(please read entire section for specific instructions):

WHO:	WHAT form:	WHERE to send:
All sites	Pregnancy Reporting [REDACTED]	Mayo Sites – attach to MCCC Electronic SAE Reporting Form Non Mayo sites – complete and forward to [REDACTED]
Mayo Clinic Sites	Mayo Clinic Cancer Center SAE Reporting Form: [REDACTED]	Will automatically be sent to [REDACTED]

Definitions

Adverse Event

Any untoward medical occurrence associated with the use of a drug in humans, whether or not considered drug related.

Suspected Adverse Reaction

Any adverse event for which there is a reasonable possibility that the drug caused the adverse event.

Expedited Reporting

Events reported to sponsor within 24 hours, 5 days or 10 days of study team becoming aware of the event.

Routine Reporting

Events reported to sponsor via case report forms

Events of Interest

Events that would not typically be considered to meet the criteria for expedited reporting, but that for a specific protocol are being reported via expedited means in order to facilitate the review of safety data (may be requested by the FDA or the sponsor).

Unanticipated Adverse Device Event (UADE)

Any serious adverse effect on health or safety or any life-threatening problem or death caused by, or associated with, a device, if that effect, problem, or death was not previously identified in nature, severity, or degree of incidence in the investigational plan or application (including a supplementary plan or application), or any other unanticipated serious problem associated with a device that relates to the rights, safety, or welfare of subjects

10.1 Adverse Event Characteristics

CTCAE term (AE description) and grade: The descriptions and grading scales found in the revised NCI Common Terminology Criteria for Adverse Events (CTCAE) version 4.0 will be utilized for AE reporting. All appropriate treatment areas should have access to a copy of the CTCAE version 4.0. A copy of the CTCAE version 4.0 can be downloaded from the CTEP web site:

([REDACTED])

- a. Identify the grade and severity of the event using the CTCAE version 4.0.
- b. Determine whether the event is expected or unexpected (see Section 10.2).
- c. Determine if the adverse event is related to the study intervention (agent, treatment or procedure) (see Section 10.3).
- d. Determine whether the event must be reported as an expedited report. If yes, determine the timeframe/mechanism (see Section 10.4).
- e. Determine if other reporting is required (see Section 10.5).
- f. Note: All AEs reported via expedited mechanisms must also be reported via the routine data reporting mechanisms defined by the protocol (see Sections 10.6 and 18.0).

NOTE: A severe AE is NOT the same as a serious AE, which is defined in Section 10.4.

10.2 Expected vs. Unexpected Events

Expected events - are those described within the Section 15.0 of the protocol, the study specific consent form, package insert (if applicable), and/or the investigator brochure, (if an investigator brochure is not required, otherwise described in the general

investigational plan).

Unexpected adverse events or suspected adverse reactions are those not listed in Section 15.0 of the protocol, the study specific consent form, package insert (if applicable), or in the investigator brochure (or are not listed at the specificity or severity that has been observed); if an investigator brochure is not required or available, is not consistent with the risk information described in the general investigational plan.

Unexpected also refers to adverse events or suspected adverse reactions that are mentioned in the investigator brochure as occurring with a class of drugs but have not been observed with the drug under investigation.

An investigational agent/intervention might exacerbate the expected AEs associated with a commercial agent. Therefore, if an expected AE (for the commercial agent) occurs with a higher degree of severity or specificity, expedited reporting is required.

